# Data Analysis:

Descriptive statistics, including frequency counts for categorical variables and measures of central tendency and dispersion for continuous variables will be calculated to summarize the data. Baseline demographic data will be compared across treatment groups. The investigators will compare baseline variables between groups by using independent t-tests or Mann–Whitney U tests for continuous data and chi-square tests of independence for categorical data. If analysis of baseline data suggests randomization did not reasonably control for potential confounders, those covariates will be included in models to adjust for confounding variables. If appropriate, statistical adjustments will be made for baseline characteristics that are significantly different between groups. An intention-to-treat analysis will be utilized, in which all participants will be analyzed in the group to which they were originally assigned. All drop-outs and the reason for dropping out of the study will be reported. An *a priori* alpha level of 0.05 will be used for all analyses. All data will be screened to ensure they meet the assumptions for the inferential statistical analyses described below. If they do not meet the necessary assumptions, appropriate nonparametric procedures will be utilized.

Specific Aims: Primary Aim #1: To determine the validity of the clinical prediction rule for identifying patients with neck pain who are likely to benefit from C-TJM. Pain and Disability. The investigators will examine the primary aim with separate random intercept linear mixed models with treatment group (MTE vs. MoE), status on the CPR (positive or negative) and time (baseline, 1-week and 4weeks) as fixed effects. The dependent variables will be pain (NPRS) and disability (NDI score). The hypothesis of interest is the group \* CPR status \* time interaction. The primary dependent variables are the 1-week NPRS and NDI scores to mirror the follow-up used in Cleland and colleagues' study. The investigators will assess the NPRS and NDI scores after 4 weeks to determine whether a patient's status on the rule predicts outcome at a longer follow-up. The investigators will perform planned pairwise comparisons at each follow-up period by using the Bonferroni test of inequality. The investigators hypothesize that patients who are positive on the rule and receive TJM will achieve greater improvement in immediate (1-week) and 4-week pain and disability, than patients who are negative on the rule and receive TJM, and compared to patients who are positive on the rule but receive an alternative exercise program without TJM. Because the rule is believed to be specific to a TJM intervention, investigators hypothesize that outcomes among those receiving the MoE treatment would not differ on the basis of a patient's status on the rule.

Secondary Aim #1: To compare the long-term (6-month) pain and disability scores (clinical

outcomes) and healthcare utilization based on status on the clinical prediction rule and the treatment received. The investigators will examine this with random intercept linear mixed models with treatment group (MTE vs. MoE), status on the CPR (positive or negative), and time (baseline and 6-months) as fixed effects. The dependent variables will be pain (NPRS) and disability (NDI) scores. The investigators will perform planned pairwise comparisons at each follow-up period by using the Bonferroni test of inequality. The hypothesis of interest is the group \* status on CPR \* time interaction. The investigators hypothesize that patients who are positive on the rule and received TJM would experience greater improvement at 6-months than patients who are negative on the rule and received the MoE program without TJM.

The investigators will also examine healthcare utilization using a two-way ANOVA comparing the number of healthcare visits post-treatment sessions with treatment group (MTE vs. MoE) and status on the clinical prediction rule (positive or negative) as independent variables. If appropriate, the interaction effect of the two independent variables will also be accounted for in the analysis. The dependent variable is the number of healthcare visits after completion of the treatment. The investigators hypothesize that patients who are positive on the rule and received TJM utilize less additional healthcare visits after completion of the treatment than patients who are negative on the rule and received the MoE program without TJM.

Secondary Aim #2: To compare changes in GROC and fear-avoidance beliefs at long-term follow-up (6-month) based on status on the clinical prediction rule and the treatment received. The investigators will examine this with separate random intercept linear mixed models with treatment group (MTE vs. MoE), status on the clinical prediction rule (positive or negative), and time (baseline and 6-months) as fixed effects. The dependent variables will be GROC changes and fear avoidance beliefs. The hypothesis of interest is the group \* status on CPR \* time interaction. The investigators will perform planned pairwise comparisons at each follow-up period by using the Bonferroni test of inequality. The investigators hypothesize that patients who are positive on the rule and received TJM would experience greater reduction in pain and fear avoidance beliefs than patients who are negative on the rule and received TJM, compared with patients who are positive on the rule but received the MoE program without TJM.

Missing Data. While analysis using mixed models allows all observed data to be included in the analysis under the assumption that the data are missing at random, if substantial missing data occurs, multiple imputation or mean conditional imputation will be used with subsequent sensitivity analyses to explore the impact of imputation on results. To address the issue of artificially reduced estimates of stochastic uncertainty produced by imputation, bootstrapping procedures will be used on the entire imputation and estimation process.

Sample Size and Power. The sample size calculation is based on the primary aim of the study. This aim looks at the change in NDI at a 1-week follow-up as the dependent variable. The investigators based sample size calculation on detecting a statistically significant difference between any of the 4 cells of

the study which include the patient's status on the rule (patients that meet the CPR and patients that do not meet the CPR) and group (MTE and MoE) by using the 1-week NDI score at an alpha-level of 0.05. To maximize statistical power, investigators will aim to include 4 equal group sizes based on the rule status (positive vs. negative) and treatment (MTE vs MoE). Based on previous research investigators expect a standard deviation of change scores on the NDI of 12 points. To detect a 10 point change in NDI at the 1-week follow up (effect size 0.80) with 90% power using a two-tailed hypothesis and assuming a 50% distribution of patients who do and do not meet the rule based on our randomized block design, 31 patients per cell are required. The investigators will recruit 140 subjects into the study to control for dropouts prior to the 1- and 4-week follow-up and possible distribution discrepancies between the classifications. This will require recruitment of approximately 12 subjects per month over a 12-month recruitment period.

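### Covariates enter through baseline significance tests or a judgement after the data are seen, and the primary model does not use baseline NDI/NPRS to sharpen the randomised comparisons

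*Combined protocol and SAP*

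**What the plan says.** Section 7.0, Data Analysis, tests baseline variables between treatment groups: "The investigators will compare baseline variables between groups by using independent t-tests", with rank and chi-square alternatives. Two triggers follow. One is a judgement: "If analysis of baseline data suggests randomization did not reasonably control for potential confounders, those covariates will be included in models". The other is a test result: "If appropriate, statistical adjustments will be made for baseline characteristics that are significantly different between groups". The section gives no covariate list, no threshold for the judgement, and no statement of whether a covariate enters as a main effect or by time.

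Primary Aim #1 fits random-intercept mixed models for NPRS and NDI with treatment group, "status on the CPR (positive or negative) and time (baseline, 1-week and 4weeks) as fixed effects". Its target is the group × CPR × time interaction, with pairwise comparisons at each follow-up. Baseline is an outcome row. It is not a covariate, and its means are not constrained to be equal between arms. The hypothesis concerns improvement: CPR-positive TJM recipients "will achieve greater improvement in immediate (1-week) and 4-week pain and disability, than patients who are negative on the rule and receive TJM".

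Sample Size and Power states that "investigators expect a standard deviation of change scores on the NDI of 12 points".

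**The concern.** Section 4.0 gives concealed 1:1 randomisation within each CPR stratum. A baseline difference between MTE and MoE is therefore chance, and its p-value says nothing about whether the variable predicts outcome. A rule that waits for significance leaves the model open until the data are seen. It will often add something, but seldom the variable that would help.

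A second matter is independent of that rule. Baseline NDI and NPRS are collected on everyone and are likely to be prognostic, yet the planned interaction only subtracts them. Subtraction is generally less efficient than adjustment. At stake are a primary model fixed in advance and precision that needs no further data. The validity of the planned contrast is not at stake.

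**Working it through.** **Inputs from the documents.** Change SD 12; target difference 10; 90% power, two-sided ("To detect a 10 point change in NDI at the 1-week follow up (effect size 0.80) with 90% power using a two-tailed hypothesis"); alpha 0.05; 31 per cell required and 35 per cell recruited; NDI minimum clinically important difference 5.5 to 7 points (Section 4.0). All NDI figures are taken to be on one scale.

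**Assumed, because the documents do not give them.** The correlation r between baseline and 1-week score (0.3 to 0.7); the ratio k = baseline SD / 1-week SD; the number of baseline variables tested; and, for the simulation of levels only, a 1-week SD of 12.

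**Plan's own figure.** n = 2 × [12 × (1.960 + 1.282) / 10]² = 30.26, so 31 per cell. The stated size is reproduced as an unadjusted two-cell comparison of change scores. At 35 per cell, power by noncentral t is 93.0%.

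**Significance trigger.**
- Chance that at least one of m independent variables is flagged: 1 − 0.95^m = 40%, 64% and 79% for m = 10, 20 and 30.
- Difference needed to be flagged at 70 versus 70: t(138) × √(2/70) = 0.33 SD.
- Simulation: 6,000 runs, 140 patients, 35 per cell, no treatment effect, one prognostic variable among 20, flagged variables added as main effects. Some variable was flagged in 64.6% of runs and the prognostic one in 4.8%.

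Sampling SD of the 1-week MTE − MoE level difference in CPR-positive patients (here r is the covariate's correlation with the 1-week score):

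| r | no adjustment | significance rule | prognostic covariate named in advance | type I error, rule |
|---|---|---|---|---|
| 0.3 | 2.865 | 2.885 | 2.748 | 0.051 |
| 0.5 | 2.864 | 2.850 | 2.495 | 0.049 |
| 0.7 | 2.864 | 2.795 | 2.057 | 0.044 |

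At r = 0.5 the rule recovers (2.864² − 2.850²) / (2.864² − 2.495²) = 0.080 / 1.978, about 4% of the available variance reduction. At r = 0.7 it recovers 0.390 / 3.971, about 10%. The judgement trigger was not simulated.

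**Primary interaction.** With complete data, the 1-week group × CPR × time contrast from the random-intercept model equals the change-score difference-in-differences (largest gap 1e-13 over 150 simulated trials). A covariate added as a main effect leaves it unchanged (largest gap 3e-13), whether the rule selects it or it is named in advance. Its SE is 12 × √(4/35) = 4.06. Constraining baseline means to be equal between arms within stratum gave a mean SE of 3.52 at r = 0.5, k = 1, in line with 4.06 × √0.75 = 3.51.

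**Gain from baseline adjustment.** Variance relative to change scores is (1 − r²) / (1 + k² − 2kr). At k = 1 this is (1 + r)/2, so the effective SD is 12 × √((1 + r)/2). Power for MTE versus MoE within a stratum, 35 per cell, noncentral t, 0.05 per comparison:

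| | change score | r = 0.7 | r = 0.5 | r = 0.3 |
|---|---|---|---|---|
| variance ratio (k = 1) | 1 | 0.85 | 0.75 | 0.65 |
| effective SD | 12 | 11.06 | 10.39 | 9.67 |
| power, 10 points | 93% | 96% | 98% | 99% |
| power, 7 points | 67% | 74% | 79% | 85% |
| power, 5.5 points | 47% | 54% | 59% | 65% |

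If baseline varies less than follow-up, the gain shrinks. At k = 0.8, power for 7 points is 68%, 72% and 78% for r = 0.7, 0.5 and 0.3. At k = r = 0.8 the ratio is 0.36 / (1 + 0.64 − 1.28) = 1, so there is no gain.

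**The case against.** The strongest reply is that nothing here is invalid. The change contrast matches a hypothesis worded as improvement, type I error stays at or below nominal, and the planned 10-point comparison already has about 93% power. All of that stands, so a reader who infers that the covariate rule produces false positives or undermines the primary test goes beyond the evidence.

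A reader might also infer that the significance rule is what costs the interaction its precision. It is not. A main-effect covariate does nothing for that contrast even when named in advance, and the table of SDs applies only if the pairwise comparisons are of 1-week levels, which Primary Aim #1 does not state.

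Nor is little recovery a universal figure. If a single covariate is tested in the same 35 versus 35 comparison that is then estimated, the rule recovers about a quarter of the true variance gain, although only about 3% of the gain in reported variance at r = 0.5. The judgement trigger may also favour prognostic variables more than a test does.

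Finally, it would be wrong to say that baseline is unused. The interaction subtracts it, and at k = 1 this beats a follow-up-only analysis when r exceeds 0.5. The entry requirement of NDI ≥ 10 truncates baseline but not follow-up, so k below 1, and hence a small gain, is quite plausible.

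**Conclusion.** The point holds as one of pre-specification and efficiency. The two triggers leave the covariate set undetermined until the data are seen, and the significance trigger is a poor way to find prognostic variables. Separately, the planned use of baseline is valid but never more precise than adjustment. At k = 1, adjustment would leave 65% to 85% of the change-score variance for r = 0.3 to 0.7. That matters for differences near the protocol's own minimum important difference and for the interaction, and little for the 10-point pairwise target. The gain depends on r and k, which the documents do not give, and may be nil. Any shortfall in power for the interaction against the stated 90% is a separate sizing question and is not part of this point. The change is worth making because it uses data already collected and costs almost nothing.

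**What to change.** In Data Analysis, delete both data-driven triggers and keep baseline comparisons descriptive. If other covariates are wanted, name them and their form (main effect or by time) before data are seen.

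In Primary Aim #1, pre-specify that baseline NDI and NPRS means are constrained equal between MTE and MoE within each CPR stratum, with an unstructured covariance over the three times. Use this for the interaction and for MTE versus MoE within a stratum. Never apply the constraint across strata, because CPR status is not randomised. Keep the change contrast for CPR-positive versus CPR-negative patients among MTE recipients. The constrained model still yields it, since each stratum keeps its own baseline mean.

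If baseline is instead a covariate (with covariate-by-time) for the 1- and 4-week scores, restate the target as the group × CPR contrast at 1 week, and at 4 weeks. Group × CPR × time would then test only whether the effect differs between those two visits.

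The cost is SAP wording and four more covariance parameters (six instead of two), or one or two degrees of freedom for a baseline covariate. No new data are needed.

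### The primary model leaves baseline means free between randomised arms and names only a random intercept: the 1-week treatment contrasts are unbiased but can lose precision, and tests at one follow-up can be miscalibrated

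*Combined protocol and SAP*

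**What the plan says.** Under Primary Aim #1 in Section 7.0, each outcome is analysed with "separate random intercept linear mixed models with treatment group (MTE vs. MoE), status on the CPR (positive or negative) and time", and the levels are given as "time (baseline, 1-week and 4weeks) as fixed effects". Baseline is therefore a response. The hypothesis of interest is the three-way interaction, which leaves the baseline mean free in each of the four cells. The paragraph goes on: "The primary dependent variables are the 1-week NPRS and NDI scores". It also calls for "planned pairwise comparisons at each follow-up period" with a Bonferroni correction. The random intercept is the only covariance feature named.

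The general Data Analysis text adds covariates if randomisation appears not to have controlled confounding, and says "statistical adjustments will be made for baseline characteristics that are significantly different between groups". On model assumptions it says: "If they do not meet the necessary assumptions, appropriate nonparametric procedures will be utilized". Section 4.0 randomises treatment within each CPR stratum.

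Sample Size and Power is based on "detecting a statistically significant difference between any of the 4 cells" and assumes a "standard deviation of change scores on the NDI of 12 points".

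**The concern.** Randomisation within strata makes the true baseline means of the two arms equal within each CPR stratum. A model that estimates them separately discards that knowledge, and the treatment contrast at 1 week reduces to a difference in mean change. Adjusting for baseline uses the same data more efficiently. Under the plan, however, baseline score enters as an adjustment only if a chance imbalance triggers it.

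The second issue is calibration. A random intercept with the usual single residual variance assumes equal variances at all visits and equal correlations between all pairs of visits. The plan draws conclusions at individual visits, with 1 week primary. If the assumption fails, those standard errors can be too wide or too narrow, and nonparametric procedures do not repair a within-patient covariance.

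At stake are some power, mainly for the interaction, and the calibration of tests at one follow-up. Bias is not at stake.

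**Working it through.** **Inputs from the plan.** Change SD 12, difference 10, two-sided alpha 0.05, 90% power, 31 per cell required, 140 recruited (35 per cell).

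**Assumed, because the documents do not give them.** Per-visit SDs, correlations between visits, and a 10-point interaction (the plan sizes a two-cell difference).

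**1. The plan's own figure.** n = 2 × 12² × (1.960 + 1.282)² / 10² = 30.3, so 31 per cell. It reproduces.

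**2. What the planned model estimates.** Fitted to complete simulated data, its 1-week treatment contrast equals the difference in mean change to rounding error (about 10⁻¹³).

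**3. Precision.** With baseline SD s0, 1-week SD s1 and correlation r, the variance ratio, adjusted to change-score, is

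s1²(1 − r²) / (s0² + s1² − 2·r·s0·s1).

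It never exceeds 1, and equals 1 only when the slope of 1-week score on baseline is 1. For equal SDs it is (1 + r)/2.

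Power uses the noncentral t with 136 degrees of freedom (140 − 4), before Bonferroni. The change SD is held at 12. The planned standard errors are 12·√(2/35) = 2.87 for two cells and 12·√(4/35) = 4.06 for the interaction, giving power 0.933 and 0.687. Adjustment multiplies the variance by the ratio.

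| s0 : s1 | r | Ratio | Two-cell power | Interaction power |
|---|---|---|---|---|
| equal | 0.4 | 0.700 | 0.985 | 0.833 |
| equal | 0.5 | 0.750 | 0.979 | 0.807 |
| equal | 0.7 | 0.850 | 0.964 | 0.756 |
| equal | 0.8 | 0.900 | 0.954 | 0.732 |
| 8 : 10 | 0.4 | 0.840 | 0.965 | 0.761 |
| 8 : 10 | 0.8 | 1.000 | 0.933 | 0.687 |
| 10 : 8 | 0.4 | 0.538 | 0.997 | 0.916 |
| 10 : 8 | 0.8 | 0.640 | 0.991 | 0.864 |

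**4. Calibration at one follow-up.** True error at nominal 5% is approximately 2·P(Z > 1.96·√(Vmodel/Vtrue)). The value of Vmodel depends on the contrast:

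- Change from baseline: Vmodel is the mean of the three pairwise change variances, and Vtrue is the change variance for that visit.
- Cell means at a visit: Vmodel is the mean of the three visit variances, and Vtrue is that visit's variance.

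Example, scenario A, change contrast: the change variances are 52 (baseline–1 week), 131.2 (baseline–4 weeks) and 100 (1 week–4 weeks), with mean 94.4. The 1-week error is 2·P(Z > 1.96·√(94.4/52)) = 0.8%. The 4-week error is 2·P(Z > 1.96·√(94.4/131.2)) = 9.6%. For cell means, the visit variances 64, 100 and 144 average 102.7, giving 4.7% and 9.8%.

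SDs below are ratios for baseline : 1 week : 4 weeks. Correlations are baseline–1 week, baseline–4 weeks, 1 week–4 weeks.

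| Scenario | SD ratio | Correlations | Change error, 1 wk / 4 wk | Cell-mean error, 1 wk / 4 wk |
|---|---|---|---|---|
| A | 8 : 10 : 12 | 0.7, 0.4, 0.6 | 0.8 / 9.6% | 4.7 / 9.8% |
| B | 8 : 10 : 12 | all 0.5 | 2.7 / 5.6% | 4.7 / 9.8% |
| C | equal | 0.4, 0.3, 0.7 | 6.5 / 8.7% | 5.0 / 5.0% |
| D | equal | all 0.5 | 5.0 / 5.0% | 5.0 / 5.0% |
| E | 10 : 8 : 8 | all 0.5 | 6.0 / 6.0% | 3.3 / 3.3% |

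Simulation of the change-contrast tests for the interaction (40,000 trials per scenario, four cells of 35) agreed within 0.3 points. The joint 2-df interaction test had error 5.1–6.1% across the five scenarios.

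**The case against.** The strongest objections are these.

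- **The planned contrast is already adequate for its stated purpose.** It is unbiased under randomisation, and at 35 per cell the two-cell power is 93% against a 90% target. This stands. Adjustment adds about 2–5 points there with equal SDs. The larger gain is for the interaction, whose 10-point size is assumed.
- **The gain may be nil.** The NDI entry floor of 10 could narrow the baseline spread, which points towards the less favourable ratio. This stands: with 8 : 10 the gain is 0–7 points for the interaction and 0–3 for two cells.
- **The error figures depend on the contrast meant.** Sample Size and Power refers both to change in NDI and to the 1-week score, so the plan does not settle it. Moving from change to cell means removes the error in C and reverses it in E. This stands, which is why both columns are shown.
- **Some scenarios are extreme.** Scaled to a 1-week change SD of 12, scenario A implies visit SDs of 13.3, 16.6 and 20.0. That is wide on the 0–50 NDI scale and less so on the doubled percentage scale; the plan does not say which unit its SD uses. This stands, so A is an illustration, not a forecast.
- **The plan does not state a residual structure, and it promises assumption checks.** True. A single residual variance is the usual reading of a random-intercept model, not a stated decision. But the only remedy named would not supply a different covariance.

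A reader might infer that the primary analysis is invalid, or that its false-positive rate is near 10%. The documents support neither. The estimate is unbiased, the highest figures belong to 4 weeks under assumed inputs, and the joint test stays close to nominal.

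**Conclusion.** The point holds as a modest one about precision and specification. Leaving baseline means free between randomised arms gives up precision in large samples unless the slope of 1-week score on baseline is 1. With equal baseline and 1-week SDs and correlation 0.8 to 0.4, adjustment takes two-cell power from 93% to 95–98% and power for a 10-point interaction from 69% to 73–83%. It does more if the 1-week SD is smaller than baseline, and may do nothing if it is larger.

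The covariance issue is secondary. In the assumed scenarios, change-from-baseline tests at nominal 5% run at about 1–6% at 1 week and 5–10% at 4 weeks. Comparisons of cell means run at about 3–5% and 3–10%. There is no error when variances and correlations are equal across visits. Only the change SD, the 10-point two-cell difference and the sample size come from the documents.

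It would also be tempting to claim the gain for every planned comparison. That is not supported. CPR status is not randomised, so for CPR-positive versus CPR-negative patients within the manipulation arm, baseline adjustment changes the question asked, and no gain is claimed.

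**What to change.** In Section 7.0, for NDI and separately for NPRS:

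- Keep baseline, 1 week and 4 weeks as outcomes.
- Constrain baseline means to be equal between treatments within each CPR stratum, and leave them free across CPR status.
- Use an unstructured within-patient covariance with Kenward–Roger degrees of freedom.
- For these primary outcomes, replace the imbalance-triggered covariate rule with this prespecified adjustment.
- State whether comparisons at each follow-up are of change from baseline or of means at that visit.

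This one model gives the baseline-adjusted interaction and the MTE versus MoE contrast within each stratum. It still gives change from baseline for CPR-positive versus CPR-negative within the manipulation arm. A model with baseline as a covariate is not a substitute for that last contrast, because it compares the strata at equal baseline scores.

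The cost is revised wording, a few degrees of freedom and slightly more analysis work. Every variable is already collected. The wording should be settled before outcome data are examined.

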  - Group assignment will be stratified via permuted block randomization implemented by a biostatistician. Ordered group assignments for each location will be provided via numbered and sealed envelopes to be opened after the baseline examination and enrollment conducted by the study coordinator/principal investigator.
  - Participants are stratified into blocks based on their status on the Clinical Prediction Rule (CPR) as either positive or negative. Within each block, participants are then randomly assigned to one of two treatment groups. This approach ensures that treatment groups are comparable in terms of key prognostic indicators, reducing selection bias.
  - The randomization process is concealed, with group assignments provided in sealed envelopes opened only after baseline assessments are completed. This prevents any potential influence on the assignment process by the researchers or participants.

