# Treatment Session #1

Cervical TJM: The patient will receive a supine cervical TJM directed to an appropriate level between C3 and C7. Clinicians will be allowed to use discretion as to which level they feel is more restricted, and they will then perform a cervical TJM technique to each side of the cervical spine. They will be allowed to perform a maximum of two attempted TJMs to each side. The investigators are intentionally selecting manipulative interventions that can easily be performed, in order to increase the generalizability of the CPR that was developed. In addition, patients will be instructed in a basic cervical mobility exercise (Appendix F) and instruction to maintain usual activity level within the limits of pain. The following is a detailed description of the steps involved in performing TJM to the cervical spine:

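### Allocation lists are issued clinic by clinic but no model includes clinic, so the non-randomised CPR+ versus CPR- comparison under TJM can be confounded by clinic.

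*Combined protocol and SAP*

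**What the plan says.** Under Randomization, section 4.0 says: "Ordered group assignments for each location will be provided via numbered and sealed envelopes". The same section names CPR status as the blocking variable, with trial totals of 70 CPR+ and 70 CPR- patients and 35 per treatment in each block. It sets no CPR mix for individual clinics.

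Section 7.0, Primary Aim #1, fits "separate random intercept linear mixed models with treatment group (MTE vs. MoE), status on the CPR (positive or negative) and time" to NDI and NPRS. The unit of the random intercept is not named. The group x CPR status x time interaction is the hypothesis of interest. Two simple comparisons are also hypothesised, there and in section 2.0: CPR+ with TJM against CPR- with TJM, and CPR+ with TJM against CPR+ with non-thrust mobilisation (NTM). The secondary models likewise omit clinic.

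The opening paragraph of Data Analysis compares baseline data across treatment groups and allows covariates to be added where randomisation appears not to have controlled confounders. Clinic is not named.

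**The concern.** CPR status is observed, not assigned, so randomisation does not balance clinic between CPR+ and CPR- patients. Several features of the plan could make the CPR mix differ by clinic:

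- Section 3.0 recruits through each clinic's own channels and its own intake.
- The same section narrows screening to symptom duration under 38 days once the CPR- blocks are filled, so a clinic recruiting late could enrol mainly CPR+ patients.
- Spring-test pain, one of the four criteria, is judged by the examiner.

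If a clinic with good early outcomes also enrols many CPR+ patients, part of its advantage is credited to the rule; the reverse pattern hides a real effect. The baseline check is unlikely to catch this. It compares treatment groups, and lists issued by clinic tend to balance clinic between those groups.

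**Working it through.** **The plan's own figure.** Inputs from Sample Size and Power: a 10-point difference, "investigators expect a standard deviation of change scores on the NDI of 12 points", two-sided alpha 0.05 and 90% power.

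n per cell = 2 x (1.960 + 1.282)^2 x (12/10)^2 = 30.26, rounded up to 31. This matches "31 patients per cell are required". No clinic term enters the calculation.

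**Assumptions not in the documents.** Four clinics of 35 (140/4). The clinic share of the variance of 1-week change (ICC) is 0.05 or 0.10. The SD of 12 is the total, so the clinic SD is 12 x sqrt(ICC) = 2.68 or 3.79 points. The CPR+ shares across the four clinics are varied. Tests are at an unadjusted 0.05.

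**Step 1: confounding in CPR+ versus CPR- under TJM.** The two groups weight the clinics differently. At shares 20/40/60/80%, CPR+ patients are spread 0.1/0.2/0.3/0.4 over the clinics and CPR- patients 0.4/0.3/0.2/0.1. The weight differences are -0.3, -0.1, 0.1 and 0.3, and the root of their summed squares is sqrt(0.20) = 0.447. At 30/40/60/70% it is sqrt(0.10) = 0.316. At equal shares it is 0.

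Confounding SD = that factor x clinic SD:

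| CPR+ shares | ICC 0.05 | ICC 0.10 |
|---|---|---|
| equal | 0 | 0 |
| 30/40/60/70% | 0.85 | 1.20 |
| 20/40/60/80% | 1.20 | 1.70 |

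The plan's target is 10 points, and the nominal SE is 12 x sqrt(2/35) = 2.87.

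**Step 2: false-positive rate.** The true SD of the contrast is sqrt[144 x (1 - ICC) x 2/35 + confounding SD^2]. Without clinic, simulation gives a mean reported SE of about 2.85 (ICC 0.05) or 2.82 (ICC 0.10). The critical t is 1.978.

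- 20/40/60/80%, ICC 0.05: true SD = sqrt(7.82 + 1.44) = 3.04; 1.978 x 2.85/3.04 = 1.85, a rate of about 6%.
- 20/40/60/80%, ICC 0.10: true SD = sqrt(7.41 + 2.88) = 3.21; 1.978 x 2.82/3.21 = 1.74, about 8%.
- 30/40/60/70%: true SD 2.92 and 2.97, about 5% and 6%.
- Equal shares: true SD 2.80 and 2.72, about 4%, so no inflation.

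Simulation of 6,000 trials per scenario at 20/40/60/80% gave 5.9% and 7.4% without clinic and 4.6% with it. A separate run at ICC 0.10 gave 7.8% and 5.4%.

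**Step 3: randomised contrast and interaction.** With allocation balanced within clinic and CPR status, additive clinic effects cancel. The model without clinic leaves clinic variance in the residual, so its SE is too large by 1/sqrt(1 - ICC): 1.026 at ICC 0.05 and 1.054 at 0.10. For TJM versus NTM within CPR+ the true alpha is 0.044 and 0.039. At 31 per cell and ICC 0.10, power is 91.8% without clinic and 93.3% with it.

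**Step 4: a TJM effect that varies by clinic.** With an assumed SD of 2 points (mild imbalance, about 40/45/55/60%) or 3 points (20/40/60/80%) and ICC 0.05, type I error for the randomised contrast is 0.062 and 0.090 without clinic. With a clinic main effect it is 0.065 and 0.095, so that term does not repair it.

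**The case against.** The strongest reply is that the plan's named hypothesis is the three-way interaction, which additive clinic effects do not bias. Support for the rule also requires CPR+ patients under TJM to beat a randomised comparator, and the plan expects no CPR difference under NTM, where the same confounding would show. In 8,000 null trials per scenario without a clinic term, CPR+ with TJM falsely beat both comparators in at most 0.7%. This stands and limits the damage. It does not remove the point. If TJM helps everyone regardless of CPR status, the randomised comparison is truly positive and only the exposed contrast separates a valid rule from an invalid one.

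The cancellation also depends on balance within clinic and CPR status. Section 4.0 stratifies by CPR, but Identification of the Status on the Rule describes assignment regardless of CPR status. If the lists are by clinic alone, the cancellation is only approximate.

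The Data Analysis text later refers to differences between groups, which could be read as the four cells. That reading is possible, but clinic is still not named.

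A reader might infer more from the omission than the documents support:

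- That the comparison is confounded. Both conditions are needed, and neither is documented.
- That the standard errors of the randomised contrasts are too small. Under additive clinic effects they are slightly too large.
- That error rates reach 8-12%. This takes 12 as the within-clinic SD and adds a clinic SD of 4 to 6 points, whereas section 7.0 gives 12 as the SD of change scores, that is, the total.
- That therapist discretion makes the case for a clinic term. "Clinicians will be allowed to use discretion as to which level they feel is more restricted" concerns the level treated, within a prescribed manoeuvre, a manual and training. Step 4 shows that a clinic main effect would not address variable delivery anyway.

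**Conclusion.** The point holds in a limited form. A stated primary comparison is not randomised, clinic is the unit to which allocation lists are issued, and no model or baseline check guards against clinic differences between CPR groups. The size is conditional: about 6-8% false positives in place of 5% under a strong imbalance, about 5-6% under a moderate one, and no inflation with equal mix. For the interaction and the randomised contrast the cost is a small conservative loss of precision, not bias.

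All ICC and CPR-mix values are assumptions. The rates come from ordinary least squares on 1-week change with an unadjusted test. The plan specifies Bonferroni comparisons within mixed models, so the rates show the scale of the problem and are not the planned test's exact error. This is a worthwhile, inexpensive correction, not a threat to the design.

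**What to change.** In section 7.0:

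1. State that the random intercept is for the participant.
2. Add clinic and clinic x time as fixed effects to every longitudinal model (NDI, NPRS, FABQ). The time interaction is needed because the outcome of interest is change.
3. Add clinic as a fixed effect to the GROC and healthcare-visit models.
4. Report CPR status by clinic.
5. Add a clinic x treatment x time sensitivity analysis, labelled exploratory. It addresses a TJM effect that varies by clinic, which items 2 and 3 do not, but about 17-18 patients per arm per clinic (35/2) gives little precision.

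The cost is SAP wording and three degrees of freedom per visit. Clinic is already known for every participant. N stays at 140: with clinic in the model, the randomised contrast needs 29 per cell at ICC 0.05 and 28 at ICC 0.10, against the stated 31.
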